6. STUDY PROCEDURES

6.1. Screening

For screening procedures see the [Schedule of Activities](#) and Assessments section ([Section 7](#)).

6.1.1. Tumor Biospecimens

6.1.1.1. Combination A, B, C and D

For Phase 1b: Archival formalin-fixed paraffin-embedded (FFPE) tissue is required if available for the first 3 patients enrolled in a cohort, including replacement patients. For additional patients enrolled in each Phase 1b cohort and Phase 2, FFPE tissue must be available from the most recent primary or metastatic tumor biopsy or resection prior to start of study therapy, taken within 1 year prior to enrollment/randomization, with no intervening systemic anti-cancer therapy. This tissue may be obtained from a de novo biopsy performed prior to study entry.

A biopsy is required between Cycle 1 Day 21 (± 4 days) and Cycle 2 Day 1 (prior to dosing) and then as clinically indicated during treatment. These on-treatment biopsies are required except in instances where the procedure poses unacceptable risks per investigator documentation.

A de novo tumor sample at End of Treatment if a patient discontinues due to disease progression is required except in instances where the procedure poses unacceptable risks per investigator documentation. The de novo tumor sample collected at the End of Treatment should be performed BEFORE initiation of subsequent anticancer therapy, preferably no later than 7 days after the End of Treatment visit.

6.1.1.2. Combination F

Baseline biopsy samples are required for all patients in Combination F.

1. Archival: Required for all patients when available.
2. De novo before first SC dose on C1D1. This is not required if an archival specimen is available from the most recent primary or metastatic tumor biopsy or resection prior to start of study therapy, with no intervening systemic anticancer therapy.

Tissue is also required to be provided if tumor biopsies are taken during the study period as standard of care. If possible, the following tissues are preferable (a) at initial diagnosis, (b) between second SC dose (C1D8) and first IT dose on C1D15, (c) between C1D22 and

C2D1 before the IT dose on C2D1, and (d) within 30 days of disease progression confirmation and before initiation of subsequent anticancer therapy.

In rare circumstances, if a patient is motivated to participate and the investigator judges that the risk associated with the baseline biopsy is not appropriate for a research setting, after consultation with the Sponsor's medical monitor, the patient may be allowed on study without a biopsy prior to start of therapy.

6.1.1.3. Sample Processing and Submission Requirements

The biopsy sample(s) should be FFPE per routine pathology practice, and the resulting FFPE tissue should be submitted to the central laboratory. FFPE tissue blocks should be provided if available and permitted by local laws and policies. If blocks cannot be provided for these reasons, then sections must be freshly cut (cut no more than 30 days prior to shipment to the central laboratory), 5 μ m thick, and mounted on positively-charged microscope slides (SuperFrost Plus glass slides are recommended). A minimum of 15 (preferably 25) slides should be provided. Core needle, excisional biopsies, or resection specimens are strongly preferred since intact tumor architecture is required for adequate assessment of CD8 and PD-L1 proximity. Tumor tissue from cytologic sampling (eg, fine needle aspiration, including FFPE cell pellet material) should only be submitted for patients for whom excisional or core needle biopsy methods are contraindicated. Additional information on tumor biospecimen collection procedures is included in the study laboratory manual.

Tumor tissue from cytologic sampling (eg, fine needle aspiration, including FFPE cell pellet material), should only be submitted for patients for whom excisional or core needle biopsy methods are contraindicated.

6.1.1.4. Selection of Lesion for Biopsy

For each biopsy, a suitable tumor lesion will be designated for biopsy by the investigator. This designation will take into account: 1) the likelihood that the lesion is representative of the tumor, 2) the likelihood that the biopsy can be accessed safely, and 3) the lesion is distinct from the target lesions being followed for measurable disease. First preference is superficial (skin, subcutaneous, lymph node), palpable lesions. For other non-superficial locations, image guided biopsies are highly preferred. Second preference is abdominal lesions. Intrathoracic lesions should not be biopsied unless the potential for pneumothorax is judged to be minimal. Biopsies from bone lesions should not be submitted.

6.2. Treatment Period

For treatment period procedures, see the [Schedule of Activities](#) and Assessments section ([Section 7](#)). For all combinations, patients clinically benefiting from study treatment without unacceptable toxicity, objective disease progression, or withdrawal of consent will be given the opportunity to continue treatment up to a maximum of 2 years from the first dose of study drugs. After 2 years of treatment, patients without other options for treatment may continue on treatment with the combination to which they have been assigned or single agent avelumab upon agreement with the Sponsor.

For the treatment period, where multiple procedures are scheduled at the same nominal time point(s) relative to dosing, the following prioritization of events should be adhered to, where possible:

- Pharmacokinetic blood specimens – obtain at the scheduled time. When multiple investigational products are administered on the same day, the pre-dose PK samples for all investigational products may be obtained at any time BEFORE an infusion of the first investigational product on the given infusion day. The acceptable window for the post-dose sample(s) is ± 10 minutes of an infusion completion.
- Electrocardiograms (ECGs) – obtain as close as possible to the scheduled time, but prior to blood specimen collection (eg, PK). In exceptional circumstances when blood sampling is not feasible before ECG measurement, the ECG measurement may be performed after the blood draws. The pre-dose ECG may be obtained any time before investigational product infusion. The acceptable window for the post-dose ECG is +30 minutes of an infusion completion.
- Blood pressure/pulse rate – may be obtained prior to or after ECG collection but must be obtained prior to blood specimen collection. The pre-dose blood pressure/pulse rate may be obtained any time before infusion of the first investigational product.
- Clinical safety laboratory tests – obtain as close as possible to the scheduled time.
- Other procedures – All other procedures should be obtained as close as possible to the scheduled time, but may be obtained before or after blood specimen collection, unless sampling is determined by the study personnel to potentially impact the results.

6.3. Follow-up

For follow-up procedures see the [Schedule of Activities](#) and Assessments section ([Section 7](#)).

Patients should be evaluated up to 90 days (30 days, 60 days, and 90 days) after last dose of investigational product(s) for safety. Patients continuing to experience toxicity following discontinuation of investigational products will continue to be followed at least every 4 weeks regardless of initiation of new anticancer treatment until resolution or determination, in the clinical judgment of the Investigator, that no further improvement is expected. Follow-up beyond 30 days after last dose of investigational products product(s) may be performed either via a clinic visit or by remote contact (eg, telephone), with subsequent clinic visits requested if any concerns are noted during the telephone call.

Physical examination, ECOG status, vital signs, and safety laboratory measurements are not required for patients who initiate new anticancer treatment, unless the patient continues to experience toxicity following discontinuation of the investigational products. Contraception check and serum/urine pregnancy tests are required for all patients who enter Follow-up regardless of initiation of subsequent anticancer therapy. Patients whose disease has not progressed at the time of treatment discontinuation will enter into disease follow-up (for tumor assessment).

Patients will be followed for survival, independently of time of disease progression or initiation of subsequent anticancer therapy, for at least 2 years after randomization of the last patient in the randomized cohorts and for at least 2 years after first dose of the last patient for the non-randomized cohorts unless lost to follow-up, consent withdrawal, or study discontinued by the Sponsor. Patients will be contacted every 3 months for survival status and subsequent anticancer treatment.

6.4. Patient Withdrawal

Patients may withdraw from treatment at any time at their own request, or they may be withdrawn at the discretion of the Investigator or Sponsor for safety or behavioral reasons, or the inability of the patient to comply with the protocol-required schedule of study visits or procedures at a given study site.

Reasons for withdrawal of study treatment may include:

- Objective disease progression by RECIST v1.1 assessment. However, patients with disease progression who are continuing to derive clinical benefit from the study treatment will be eligible to continue study treatment, provided that the treating physician has determined that the benefit/risk for doing so is favorable (See [Section 5.3.5.3](#) for details and exceptions);
- Global deterioration of health status requiring discontinuation;
- Unacceptable toxicity. If the unacceptable toxicity is attributed to 1 or more of the investigational products, the Investigator (in discussion with the Sponsor) may discontinue only the causal investigational product(s) and continue treatment with the other investigational product(s);
- Pregnancy;
- Significant protocol violation;
- Lost to follow-up;
- Patient refused further treatment;
- Study terminated by Sponsor;
- Death.

Reasons for withdrawal from study follow-up may include:

- Completed study follow-up;
- Study terminated by Sponsor;

- Lost to follow-up;
- Refused further follow-up;
- Death.

If a patient does not return for a scheduled visit, every effort should be made to contact the patient. All attempts to contact the patient and information received during contact attempts must be documented in the patient's medical record. In any circumstance, every effort should be made to document patient outcome, if possible. The investigator should inquire about the reason for withdrawal, request that the patient return for a final visit, if applicable, and follow-up with the patient regarding any unresolved AEs.

If the patient refuses further visits, the patient should continue to be followed for survival unless the patient withdraws consent for disclosure of future information or for further contact. In this case, no further study specific evaluations should be performed, and no additional data should be collected. The sponsor may retain and continue to use any data collected before such withdrawal of consent.

7. ASSESSMENTS

Every effort should be made to ensure that the protocol-required tests and procedures are completed as described. However, it is anticipated that from time to time there may be circumstances, outside of the control of the investigator that may make it unfeasible to perform the test. In these cases the investigator will take all steps necessary to ensure the safety and well-being of the patient. When a protocol-required test cannot be performed, the investigator will document the reason for this and any corrective and preventive actions that he or she has taken to ensure that normal processes are adhered to as soon as possible. The study team will be informed of these incidents in a timely fashion.

7.1. Safety Assessments

Safety assessments will include collection of AEs, serious adverse events (SAEs), vital signs and physical examination, ECG (12-lead), laboratory assessments, including pregnancy tests and verification of concomitant treatments. The results of safety assessments potentially requiring dose modifications must be reviewed prior to dosing as specified in [Section 7.1.4](#).

7.1.1. Pregnancy Testing

For female patients of childbearing potential, a serum or urine pregnancy test, with sensitivity of at least 25 mIU/mL, and assayed in a certified laboratory, will be performed on 2 occasions prior to starting study treatments; once at the start of screening and once at the baseline visit, immediately before study drugs administration. Following a negative pregnancy test result at screening, appropriate contraception must be commenced and another negative pregnancy test result will then be required at the baseline visit before the patient may receive the investigational products. Additional pregnancy tests (serum or urine) will also be routinely repeated at every cycle, prior to dosing, during the active treatment period, at the end of treatment, during follow-up (up to 90 days after last study treatment), and

additionally whenever 1 menstrual cycle is missed or when potential pregnancy is otherwise suspected. In the case of a positive human chorionic gonadotropin (hCG) test, the patient will be withdrawn from study drugs but may remain in the study.

Additional pregnancy tests may also be undertaken if requested by institutional review boards/ethics committees (IRB/ECs) or if required by local regulations.

7.1.2. Contraceptive Check

Male patients who are able to father children and female patients who are of childbearing potential, if sexually active and at risk for pregnancy with their partner(s), will need to affirm that they meet the criteria for correct use of the selected method of contraception. The investigator or his or her designee will discuss with the patient the need to use at least 1 highly effective contraception method consistently and correctly and document such conversation in the patient's chart. In addition, the investigator or his or her designee will instruct the patient to call immediately if selected contraception method is discontinued, or if pregnancy is known or suspected in the patient or the patient's partner.

7.1.3. Adverse Events

Assessment of AEs will include the type, incidence, severity (graded by the NCI CTCAE version 4.03) timing, seriousness, and relatedness.

Adverse events that occur during the study will be recorded on the adverse events CRF page.

7.1.4. Laboratory Safety Assessments

Hematology and blood chemistry will be drawn at the time points described in the [Schedule of Activities](#) and analyzed at local laboratories. They may also be performed when clinically indicated. The hematology, blood chemistry, and pregnancy test (if applicable) results must be available and reviewed by the treating physician prior to study treatment administration. Further details are presented in [Section 5.3.7](#). The required laboratory tests are listed in Table 26.

Table 26. Laboratory Tests

Hematology	Chemistry	Coagulation	Urinalysis	Pregnancy Test	Other
Hemoglobin	ALT	INR			
Platelets	AST	aPTT			
WBC	Alk Phos				
Absolute Neutrophils	Sodium				
Absolute Lymphocytes	Potassium				
Absolute Monocytes	Magnesium		Urine dipstick for urine protein: If positive collect 24-hr and microscopic (Reflex Testing)	For female patients of childbearing potential, serum or urine (to be specified in the protocol)	HBV surface antigen Anti-HCV antibody If Anti-HCV antibody positive, then HCV RNA testing
Absolute Eosinophils	Chloride		Urine dipstick for urine blood: If positive collect a microscopic		

Hematology	Chemistry	Coagulation	Urinalysis	Pregnancy Test	Other
Absolute Basophils	Total Calcium		(Reflex Testing)		
	Total Bilirubin ^a				Thyroid Function Tests: TSH, free T4
	BUN or Urea				Other Tests: ACTH
	Creatinine				Morning, cortisol ^b
	Glucose (non-fasted)				Corticotropin (ACTH) stimulation test ^c
	Albumin				
	Phosphorous or Phosphate				
	Amylase				
	Gamma glutamyl transferase				
	Creatine kinase				
	Lipase				

Note:

- a. For potential Hy's Law cases, In addition to repeating measurements of AST and ALT and total bilirubin, laboratory tests should include albumin, creatine kinase (CK), direct and indirect bilirubin, gamma glutamyl transferase (GGT), prothrombin time (PT)/international normalized ratio (INR), total bile acids, alkaline phosphatase and acetaminophen drug and/or protein adduct levels.
- b. Morning, cortisol required at Screening and when clinically indicated (adrenal insufficiency suspected) for Combination F patients. Blood sample should be drawn with ACTH.

c. Serum cortisol response to acute ACTH stimulation with a 250 µg dose should be performed to establish the diagnosis of adrenal insufficiency if basal morning ACTH and cortisol results are suggestive of adrenal insufficiency (eg, cortisol level is low) at Screening and when clinically indicated for Combination F patients. Institutional standards should apply.

Abbreviations: ACTH=adrenocorticotrophic hormone, ALT=alanine aminotransferase, aPTT = activated partial thromboplastin time; AST=aspartate aminotransferase, BUN=blood urea nitrogen, CRP=C-reactive protein, HBV= hepatitis B Virus, HCV= hepatitis C Virus, INR=international normalized ratio, LDH=lactate dehydrogenase, PT=prothrombin time; TSH=thyroid-stimulating hormone, WBC=white blood cell.

7.1.5. Vital Signs and Physical Examination

Patients will have a physical examination to include major body systems, supine or sitting blood pressure, pulse rate, assessment of ECOG performance status, and height (height will be measured at screening only) at the time points described in the [Schedule of Activities](#).

Weight for the purposes of dose calculation will be recorded at screening and within 3 days pre-dose Day 1 of each cycle. Weight will not be collected at End of Treatment.

7.1.6. (12-Lead) Electrocardiogram

A standard 12-lead (with a 10-second rhythm strip) tracing will be used for all ECGs.

All patients require a single ECG measurement at screening and End of Treatment (EoT) visit. On-treatment ECGs will be performed on Day 1 of Cycles 1 and 2, before and at the end of study treatment administration. At each time point, three (3) consecutive 12-lead ECGs (triplicates) will be performed approximately 2 minutes apart to determine mean QTc (average of triplicates). When coinciding with blood sample draws for PK, the ECG

assessment should be performed prior to blood sample collection, such that the blood sample is collected at the nominal time. If patient experiences a cardiac or neurologic AE (specifically syncope, dizziness, seizures, or stroke) triplicate ECGs should be obtained at time of the event. If the mean QTc is prolonged (>500 msec), the ECGs should be re-evaluated by a qualified person at the institution for confirmation and repeated as clinically indicated. Additional triplicate ECGs may be performed as clinically indicated. Clinically significant findings seen on follow-up ECGs should be recorded as adverse events.

To ensure safety, if there is finding of QTc >500 msec (ie, $>$ CTCAE Grade 2), ECG must be reviewed by qualified personnel at the site as soon as the finding is made, including verifying that the machine reading is accurate and that the Fridericia correction formula is applied. If manual reading verifies a rate corrected QTc of >500 msec, repeat ECG should be immediately performed at least two times approximately 2 to 4 minutes apart.

An electronic reading of prolonged QTc must be confirmed by manual reading. Prior to conclusion that an episode of prolongation of the QTc interval is due to study treatment, thorough consideration should be given to potential precipitating factors (eg, change in patient clinical condition, effect of concurrent medication, electrolyte disturbance) and possible evaluation by specialist. If QTc interval reverts to less than 500 msec, and in the judgment of investigator and sponsor is determined to be due to a cause other than study treatment, then treatment may be continued with regular ECG monitoring.

7.2. Pharmacokinetics Assessments

All efforts will be made to obtain the PK samples at the scheduled nominal time relative to dosing. However, the post-dose samples obtained within ± 10 min window relative to the end of infusion (eg, between 50-70 min of infusion start for 60 minute sample) will be considered Protocol compliant. The exact time of the sample collection is noted on the source document and data collection tool (eg, CRF). The pre-dose samples can be taken at any time before infusion start. When multiple investigational products are administered on the same day, the pre-dose PK samples for all investigational products may be obtained at any time BEFORE the infusion of first investigational product on the given infusion day. If the infusion of avelumab is interrupted due to AE, the PK sample associated with that dose is not required. If a scheduled blood sample collection cannot be completed for any reason, the missed sample time may be re-scheduled with agreement of clinical investigators, patient and Sponsor.

Details regarding the collection, processing, storage and shipping of the blood samples will be provided to the investigator site prior to initiation of the trial. Samples will be analyzed using a validated analytical method in compliance with Pfizer standard operating procedures. The samples must be processed and shipped as indicated to maintain sample integrity. Any deviations from the processing steps (eg, sample collection and processing steps, interim storage or shipping conditions), including any actions taken, must be documented and reported to the sponsor. On a case by case basis, the sponsor may make a determination as to whether sample integrity has been compromised. Any deviation from the specified sample handling procedure resulted in compromised sample integrity, will be considered a protocol deviation. **CCI**

CCI

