- To assess the antitumor activity of avelumab and other immune modulators when given in combination in patients with locally advanced or metastatic solid tumors;
- To assess the correlation of antitumor activity of avelumab and other immune modulators with immune biomarkers in baseline tumor tissue.

Exploratory Objectives

- CCI

- CCI

Primary Endpoints

- Phase 1b lead-in:
 - First 2 Cycles Dose Limiting Toxicity (DLT) for Combination A, B, C and D;
 - First Cycle DLT(s) for Combination F only.
- Phase 2: Confirmed OR, as assessed by the Investigator using RECIST v1.1.

Secondary Endpoints

- Adverse events as characterized by type, severity (as graded by National Cancer Institute Common Terminology Criteria for Adverse Events [NCI CTCAE] v.4.03), timing, seriousness, and relationship to study treatments;
- Laboratory abnormalities as characterized by type, severity (as graded by NCI CTCAE v.4.03) and timing;
- PK parameters (C_{max} and C_{trough});
- Anti-drug antibody (ADA) levels;

- Time-to-event endpoints including time to tumor response (TTR), duration of response (DR), progression-free survival (PFS) as assessed by the Investigator using RECIST v1.1, and overall survival (OS);
- Confirmed OR during Phase 1b, as assessed by the investigator using RECIST v1.1;
- Biomarkers such as PD-L1 expression and tumor infiltrating CD8+ T lymphocytes in baseline tumor tissue.

Exploratory Endpoints

- CCI

- CCI

Study Design and Sample Size:

This is a Phase 1b/2, open-label, multi-center, multiple-dose, safety, clinical activity, PK, and PD study of avelumab in combination with other immune modulators in adult patients with locally advanced or metastatic solid tumors (eg, non-small cell lung cancer [NSCLC], melanoma, squamous cell carcinoma of the head and neck [SCCHN], triple-negative breast cancer [TNBC], gastric cancer, ovarian cancer, bladder cancer, or small cell lung cancer [SCLC]). In Phase 1b and Phase 2, enrollment criteria vary by tumor type and are described in detail in [Section 4.1](#). Incorporation of the other immune modulators into this study is based on preclinical and clinical data supportive of single-agent tolerability and potential clinical benefit, as well as non-clinical data suggesting safety, tolerability and clinical benefit of the agent(s) in combination with avelumab. Combinations of avelumab plus other immune modulator(s) to be evaluated are as follows:

- Combination A: avelumab plus utomilumab (4-1BB agonist mAb);

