1.2.3.5. Pharmacokinetics of PF-04518600

As of 27 October 2017, preliminary PK data were available for 52 patients at the 0.01, 0.1, 0.3, 1.5, 3, and 10 mg/kg dose levels from the monotherapy dose escalation phase (Part A1) of the B0601002 study.

Following single IV infusion of PF-04518600, PF-04518600 peak concentrations were observed at the end of infusion or at 3 hours after the end of infusion, followed by a decline in PF-04518600 concentrations exhibiting multiphasic disposition characteristics. At the 0.1 mg/kg dose, PF-04518600 PK profiles exhibited a pattern consistent with target mediated drug disposition compared with higher doses. The exposure (AUC τ) during the first cycle following PF-04518600 administration increased with increasing dose levels in an approximately dose-proportional manner between the doses of 0.3 and 10 mg/kg. The mean t $\frac{1}{2}$ values ranged from 4 to 10.1 days at the dose range of 0.1 to 10 mg/kg.

Following multiple IV infusions of PF-04518600 once every 14 days, the mean (\pm standard deviation) accumulation ratios (calculated as AUC τ , Cycle 3/AUC τ , Cycle 1) were 1.4 \pm 0.5, 1.7 \pm 0.4, 1.8 \pm 0.2, 2.0 \pm 0.2, and 2.0 \pm 0.3 at the dose levels of 0.1, 0.3, 1.5, 3, and 10 mg/kg, respectively, based on a total of 28 patients with full PK profiles from both Cycle 1 and Cycle 3.

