Avelumab, utomilumab, and PF-04518600 are to be administered as a 1-hour IV infusions; PD 0360324 is to be administered as a 30-minute IV infusion. Sites should make every effort to target infusion timing to be as close to the duration specified for the investigational product as possible. However, the 1-hour infusion(s) administered over 50-80 minutes will be considered protocol compliant. The accepted window for a 30 min infusion is ± 10 minutes. The exact duration of infusion should be recorded in both source documents and CRFs. Dose reduction for toxicity management for any of the investigational products is not permitted, however next cycle administration may be omitted due to persisting toxicity as described in [Table 21](#) and [Section 5.3.7.2](#).

The dose amount required to prepare the dose for weight-based infusion solutions (ie, avelumab and PF-04518600) will be based on the patient's weight in kilograms (kg). All patients should be weighed within 3 days prior to dosing for every cycle. If the patient experienced either a weight loss or gain $>10\%$ compared to the weight used to calculate the prior dose, the amount of investigational product required for preparation and administration for the current cycle must be recalculated using this most recent weight obtained. If weight change is $\leq 10\%$ compared to the weight used to calculate the prior dose, dose recalculation is optional and the site should follow their standard practice.

CMP-001 will be administered initially as 2 weekly SC doses followed by IT dosing at weekly intervals for 5 additional doses. After the first 7 doses, CMP-001 will be administered IT every 2 weeks (Q2W) (all cohorts). From C2D1, if IT administration is not feasible then CMP-001 should be administered in the peritumoral region. If peritumoral administration is not feasible, then SC administration in an area of the draining lymph node where primary disease exists should be implemented. If any of the above is not feasible, then SC (either arm, thigh, or anterior abdominal wall) administration should be implemented. CMP-001 administration and requirements are summarized in Table 20.

Table 20. CMP-001 Administration and Requirements

Visit/Dose	CMP-001 Administration ^a		Premedications	Post injection Observation Period
C1D1 and C1D8	SC (either arm, thigh or anterior abdominal wall)	Weekly	Mandated	Required (4 hrs)
C1D15, C1D22, C2D1, C2D8	IT ^b	Weekly	Mandated	Required (4 hrs)

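### The post-dose PK window opens 10 minutes before the infusion ends, so mid-infusion samples are compliant and can pull Cmax down but not up

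*Protocol*

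**What the plan says.** Cmax and Ctrough are secondary endpoints (Section 2.2), and Section 9.5.1 summarises both descriptively. Cmax rests on one post-dose sample per drug on each sampling day, nominally at the end of infusion (PK footnotes of the Schedule of Activities).

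The tolerance around that time is symmetric:

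- Section 7.2 sets 10 minutes either side of the end of infusion and illustrates it with "between 50-70 min of infusion start for 60 minute sample) will be considered Protocol compliant".
- Section 6.2: "The acceptable window for the post-dose sample(s) is ± 10 minutes of an infusion completion".
- The ECG footnotes for Combinations B, C and D (footnote 15) and the PK footnotes for Combination F (footnotes 28 to 30) carry the same 10 minutes.

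Section 5.3.5.1 lets the infusion length itself vary. For avelumab, utomilumab and PF-04518600, "the 1-hour infusion(s) administered over 50-80 minutes will be considered protocol compliant". For PD 0360324, "The accepted window for a 30 min infusion is ± 10 minutes", which means 20 to 40 minutes. The exact infusion duration (Section 5.3.5.1) and the exact sample time (Section 7.2) are both recorded on the CRF.

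By contrast, the post-dose ECG window in Section 6.2 is one-sided: "The acceptable window for the post-dose ECG is +30 minutes of an infusion completion".

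**The concern.** During a constant-rate infusion the concentration is still rising. A sample drawn before the end misses the drug not yet given, so it cannot be the peak. The two halves of the window do not balance. An early draw can lose a sizeable fraction of the peak, while a draw up to 10 minutes late loses almost nothing when half-lives run to days. The protocol's own data agree on direction: for PF-04518600, "peak concentrations were observed at the end of infusion or at 3 hours after the end of infusion", and not earlier.

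At stake is a one-directional error in the Cmax values behind a secondary endpoint, with added spread between patients because some are sampled early and others are not. Ctrough is unaffected, and no DLT or ORR decision depends on these values.

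**Working it through.** **Inputs**

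- Window: 10 minutes either side of the end of infusion (Sections 6.2 and 7.2).
- Permitted infusion length T: 50 to 80 minutes for the 1-hour drugs, 20 to 40 minutes for PD 0360324 (Section 5.3.5.1).
- Half-lives: PF-04518600, 4 to 10.1 days, so 96 h at the shortest (Section 1.2.3.5). Utomilumab, 136 to 179 h in Study B1641003 and 208 to 349 h in Portion A of Study B1641001 (Section 1.2.2.5). The longer values reported with rituximab would only shrink the late-draw loss below.
- Accumulation ratio R: 1.4 to 2.0 by dose for PF-04518600, based on AUC (Section 1.2.3.5).

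No half-life is visible for avelumab or PD 0360324.

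**The plan's own figure.** 60 − 10 = 50 and 60 + 10 = 70 minutes from the start, which reproduces the Section 7.2 example.

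**Early draw, first dose.** With constant-rate input, one compartment and k = ln 2 / half-life, the ratio of the concentration at time t to that at the end T is (1 − exp(−kt)) / (1 − exp(−kT)). Over these short times that is very nearly t/T, so a sample d minutes early is low by d/T, at most 10/T:

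| Infusion length (min) | Largest shortfall, 10/T |
|---|---|
| 80 | 12.5% |
| 60 | 16.7% |
| 50 | 20.0% |
| 40 | 25.0% |
| 30 | 33.3% |
| 20 | 50.0% |

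Results change by no more than about 0.1 percentage point for half-lives between 96 and 349 h.

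**Late draw.** The loss at +10 minutes is 1 − exp(−10k): 0.12% at 96 h, 0.08% at 136 h and 0.03% at 349 h. A distribution phase would add to this.

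**Average over the window.** If draw times were uniform over the 20 minutes, half would be early, by 5 minutes on average. The mean shortfall is then about ½ × 5/T = 2.5/T:

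- T = 60: 2.5/60 = 4.2%
- T = 30: 2.5/30 = 8.3%
- T = 20: 2.5/20 = 12.5%

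Among early draws alone it is 5/60 = 8.3% for a 60-minute infusion.

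**Later cycles.** Drug from earlier doses is already present, so the same absolute deficit is divided by a higher peak and the maximum becomes (10/T)/R. For T = 60 this is 16.7/1.4 = 11.9% down to 16.7/2.0 = 8.3%. Applying an AUC-based ratio to Cmax is an approximation.

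**The case against.** The strongest reply is that 10 minutes is a compliance tolerance and not a target. Section 7.2 asks sites to make every effort to sample at the nominal time, which is the end of infusion. Sample time and infusion duration are both recorded, so early samples can be identified, and the SAP, which is not shown, may already exclude them. When a post-dose ECG coincides with the PK draw, the ECG normally comes first and its window opens only at completion, so many draws will in practice fall after the infusion. Combination F is the only combination with enrolment still planned, and its infusions all last 1 hour, so rewording cannot change the 33% to 50% case prospectively.

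Most of this stands, and it limits the size of the problem. It does not remove it. The window is a protocol rule that sites follow, and effort to hit the nominal time does not make an early draw non-compliant. An SAP exclusion could discard a mistimed sample but could not recover the peak, because that sampling day has no second post-dose sample.

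A reader might also infer four stronger things that the protocol does not support:

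- **That Cmax as an endpoint is understated by 17% to 50%.** Those figures are limits for a single first-dose sample at the extreme early edge. A cohort mean would move far less.
- **That a 50-minute draw in an 80-minute infusion is compliant, reading 50/80 = 62.5% of the peak.** Sections 6.2 and 7.2 tie the window to the end of infusion, so an 80-minute infusion gives 70 to 90 minutes. The example is for a 60-minute sample.
- **That the ECG and PK windows conflict.** They share the period from completion to +10 minutes, and Section 6.2 allows the ECG after the blood draw in exceptional circumstances.
- **That comparisons across drugs or doses are distorted.** Table 19 gives every dose of a drug the same infusion length. Section 9.5.1 plans no Cmax comparison between drugs and does not say that accumulation or linearity is computed from Cmax.

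**Conclusion.** The point holds at modest size. The protocol makes mid-infusion samples compliant, and their error can only lower Cmax. The first-dose maximum per sample is about 17% for a 60-minute infusion (12.5% to 20% over 80 to 50 minutes) and about 33% for PD 0360324 at 30 minutes. The 50% case needs PD 0360324 run at its shortest permitted length and sampled at the extreme edge. The likely effect on a first-dose mean is nearer 4% and 8%, and smaller in later cycles.

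This rests on constant-rate infusion, one-compartment kinetics and, for the means, uniform draw times. The actual draw times are unknown. For avelumab and PD 0360324 it also assumes half-lives long relative to 10 minutes, since none is visible. It is worth correcting because a stated rule builds in a one-directional error that costs almost nothing to remove.

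**What to change.** 1. In Sections 6.2 and 7.2 and the Schedule of Activities footnotes that carry the tolerance, make the post-dose PK window one-sided: from completion of infusion to +10 minutes.
2. Replace the 50-to-70-minute example in Section 7.2 with one counted from the actual end of infusion.
3. Flag, or exclude from Cmax summaries, any sample whose recorded time precedes the recorded end of its infusion. This also covers samples already collected, including those from Combination C.

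The cost is a few sentences and one data-handling rule, a slightly narrower window for sites, and the loss of some early samples from Cmax summaries. No extra blood draws are needed.
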